5.2. Handling of Dropouts, Missing Data, and Outliers

5.2.1. Handling of Missing Efficacy Data

Subjects with missing HiSCR75 assessments at Week 16 will be imputed as non-responders (non-response imputation or NRI). A composite strategy will be used for intercurrent events of receiving oral antibiotic therapy that could affect HS. A list of all oral antibiotic therapy that results in such imputation will be finalized after review of all oral antibiotic therapy received by any subject and before unblinding of the study, and will include tetracycline,

clindamycin, and possibly other products. Such subjects will be imputed using NRI. The number of subjects imputed with NRI will be tabulated with reasons for imputation at Week 16.

To assess the sensitivity of the results, additional analyses will be performed where the response for HiSCR75 for all subjects will be used for sensitivity analysis, regardless of receipt of oral antibiotic therapy. Another sensitivity analysis will impute non-response for any subject who received any new oral antibiotic or an increased dose of oral antibiotic before Week 16.

For continuous efficacy endpoints, inference will be done using mixed-effects models repeated-measures⁴, which is robust to missing outcomes that are missing at random (MAR) or missing complete at random (MCAR).

The secondary endpoints of the percentage of subjects who experience HS flare and the percentage of subjects who achieved AN count of 0, 1, or 2 among participants with baseline Hurley Stage II will be analyzed analogously to the primary endpoint. Subjects who have missing data at Week 16 or who received an oral antibiotic that could impact HS will be included in the analysis as non-responders with NRI (did experience HS flare, or did not achieve AN count of 0, 1, or 2).

5.2.2. Handling of Missing Safety Data

In general, missing clinical laboratory data, vital signs, and ECG data will not be imputed. Adverse event imputations for missing severity or relationship are given in Section 6.7.2. Unknown or partial medication and AE date imputations are given below and are to be used only for the assessment of prior/concomitant status for medications and treatment-emergent status for AEs.

5.2.3. Handling of Partial and Missing Dates for Date of Birth, Adverse Events, Prior/ Concomitant Medications

Partial and Missing Dates of Birth

Where the Date of Birth is missing the following convention will be used:

Where the day is missing and month and year are available the day will be completed as the 15th. For example, Date of Birth specified as --JAN1980 will be completed as 15JAN1980.

Missing or Partial Adverse Event and Prior/Concomitant Medication Start/Stop Dates

Missing and/or incomplete dates for medications and AEs are imputed in a manner resulting in the earliest onset or the longest duration during the Treatment Period, whilst ensuring that the start date does not occur after the stop date. The stop date will not be imputed if the medication or AE is "Ongoing". Technically, this will be done as follows:

For a missing/incomplete start date/time the earliest date/time of the following will be imputed:

- The later date of: the earliest possible start date/time, and the date/time of the first dose of treatment.
- The latest possible start date/time.
- The latest possible stop date/time.

For a missing/incomplete stop date/time the later date/time of the following will be imputed:

- The earlier date/time of the latest possible stop date/time and the date/time of last dose of treatment.
- The earliest possible stop date/time.
- The earliest possible start date/time.

Here, the earliest possible date/time is defined as:

- The date/time itself if available.
- The date/time of the first day of the month at 00:00hrs, if month and year are available but the day/time is missing.
- The date/time of the first day of the year at 00:00hrs, if year is available but day/time and month are missing.
- 00:00hrs on the day of informed consent, if the date/time is completely missing.

The latest possible date/time is defined as:

- The date/time itself if available.
- The date/time of the last day of the month at 23:59hrs, if month and year are available but the day/time is missing.
- The date/time of the last day of the year at 23:59hrs, if year is available but day/time and month are missing.
- 23:59hrs on the date of last known date on the study for the subject plus one year, if the date/time is completely missing.

5.2.4. Handling of Plasma Concentrations that are Below the Lower Limit of Quantification

Plasma concentrations that are below the limit of quantification (BLQ) will be handled as follows for descriptive statistics:

- Pre-dose concentrations that are BLQ will be treated as zero.
- Post-dose concentrations that are BLQ will be treated as missing elsewhere.
- Values below the limit of quantification (BLQ) that are set to 0 in the source dataset will be treated as 0 in the calculation of summary statistics.
- Missing values will be excluded from the calculation of means, and n will reflect the actual number of values used in the calculation.
- Arithmetic mean or median values that are BLQ will be presented as 0.
- If any pre-dose BLQ results (treated as 0) are in a series of summarized data, geometric mean and coefficient of variation (CV) % of geometric mean will be reported as not calculated (NC).

6. Statistical Methods

6.1. General Principles

All data processing, summarization, and analyses will be performed using

's SAS Environment/Version 9.4 (or later) of the SAS[®] statistical software package. When data are collected both in IRT and EDC, all data for summaries and analyses will come from the EDC unless it is specifically stated that a particular data point will come from IRT.

The default summary statistics for quantitative variables will be the number of observations (n), mean, standard deviation (SD), median, minimum (min), and maximum (max), for those subjects with data.

For qualitative variables, the number (n) and percentage (%) of subjects with non-missing data per category will be the default summary presentation, and where appropriate and present, the number of missing values as a "Missing" category. The number of subjects in the analysis population will be used as denominator for percentages calculation, unless stated otherwise in TFLs mock shell(s).

The treatment group labels and presentation order are given below:

Part A	1

Full treatment group label:	Short treatment group label:	Treatment group ordering:
Open label izokibep 160 mg QW from Day 1/week 0 to Week 31	Open label Izokibep 160 mg QW	1

Part B

Full treatment group label:	Short treatment group label:	Treatment group ordering:
Placebo SC Q2W Week 0 to Week 14;		
Izokibep SC 160 mg Q2W Week 16 to Week	Placebo Q2W-	
30	Izokibep Q2W	1
Placebo SC QW Week 0 to Week 15; Izokibep	Placebo QW-	
SC 160 mg QW Week 16 to Week 31	Izokibep QW	2

Placebo SC QW Week 0 to Week 15; Izokibep SC 160 mg QW Week 16 to Week 31		
or		
Placebo SC Q2W Week 0 to Week 14; Izokibep SC 160 mg Q2W Week 16 to Week 30	Combined Placebo - Izokibep QW or Q2W	3
Izokibep SC 160 mg Q2W Week 0 to Week 30	Izokibep SC 160 mg Q2W	4
Izokibep SC 160 mg QW Week 0 to Week 31	Izokibep SC 160 mg QW	5

All statistical comparisons will be made using two-sided tests at the $\alpha = 0.05$ significance level unless specifically stated otherwise. All null hypotheses will be of no treatment difference. All alternative hypotheses will be two-sided.

All laboratory test results will be received from the central/local laboratories, and the results will be provided in either standard internal (SI) or conventional units, or both. For the TFLs, the results will be summarized or presented in International System of Units (SI) units. Refer to Appendix of the TLFs mock shells for the SI unit corresponding to each laboratory test. Refer to Appendix of the TLF shells for the precision level in which each laboratory test is reported by the central laboratories.

Specifications for table, figures and data listing formats can be found in the TFL shells specifications for this study. Refer to "2. General Format Guidelines" section within TFL shells for more details on presentation of results.

Data from Parts A and B will be summarized separately. Objectives and statistical hypotheses will be addressed using data from Part B only. The treatment policy estimand will be used in general for efficacy data, with all treated subjects contributing to Part A and all randomized subjects contributing to Part B. All treated subjects will contribute to safety analyses in both Parts A and B.

For comparisons of izokibep to placebo in Part B, the two dosing regimens of izokibep (QW and Q2W) will be compared separately to placebo. The 2 placebo dosing regimens (QW and Q2W) will be combined for comparison to each izokibep dosing regimen. Binary endpoints including the primary endpoint of HiSCR75 will be compared with a stratified test of risk difference. Continuous endpoints will be compared with a repeated measures mixed model.

Safety data will be summarized separately for Part A and Part B. Adverse events, serious adverse events, and laboratory data will be summarized.

6.2. Subject Disposition and Data Sets Analyzed

Subject disposition will be summarized by treatment group and overall for the All Screened Set. The following information will be reported:

- Number of subjects for the following categories:
 - Screened
- Number and percentage of subjects for the following categories:
 - Enrolled (Part A)/Randomized (Part B)
 - o Treated
 - Not Treated
 - Completed the study
 - Ongoing in the study
 - Discontinued the Study
 - Reasons for study discontinuation
- Number and percentage of subjects included in, and excluded from, each study population together with the reasons for exclusion from the analysis set
- Number and percentage of subjects who completed/discontinued treatment by period, including the reasons for treatment discontinuation
- Number and percentage of subjects who met/did not meet all eligibility criteria, together with the criteria not met
- Number and percentage of subjects who failed screening prior to enrollment (Part A)/randomization (Part B), including the primary reason for screen failure
- Number and percentage of subjects at each region (and each country within region)
 - Regions are defined using the following countries:
 - North America (US or Canada)
 - Europe (Spain, Hungary, Poland, or Germany)
 - Non-US (Spain, Hungary, Poland, Germany, or Canada)
- Number and percentage of subjects by stratification factors (Part B only). Each stratification variable will be presented by the stratum collected in Interactive Voice/Web Response System (IXRS)

A subject will be regarded as having completed the study if the status recorded on the End of Study CRF form is Complete, or assessments at Week 45 have been completed. A subject will be considered as having discontinued the study if they have an CRF status of premature study discontinuation. Otherwise, the subject will be considered as ongoing study.

A listing of all subjects with their treatment and study completion status, including the respective reasons for treatment discontinuation will be presented for all subjects enrolled (Part A) and randomized (Part B) in the FAS.

Final, Version 3.0, 03APR2024

Page 30 of 75 ST-AD-008 version 06 A listing of all screen failed subjects with their reasons for screen failure will be presented for the All Screen Set. A separate listing of subjects who failed at least one inclusion/exclusion criteria including a text description of the criterion failed will be presented for the All Screen Set. Subjects who screen failed will be assigned to Part A if the subject was screened at a site in the United States and the date of screen fail is before 27-Jul-2022 and assigned to Part B if the screen fail date is on or after 27-Jul-2022 or the subject was screened at a site outside of the United States.

A listing of all randomized subjects from Part B with their randomization details, including first dose date and time, and actual treatment received will be presented for the FAS.

A listing of all enrolled (Part A) and randomized (Part B) subjects excluded from the FAS will be presented.

6.3. Protocol Deviations

All important protocol deviations will be summarized for the FAS for Part A (overall) and Part B by treatment group and overall as described below:

• The number of unique subjects with at least one important protocol deviation as well as the number of subjects in each important protocol deviation category will be presented by default descriptive summary statistics for categorical variables.

A listing of all subjects with one or more protocol deviations will be presented for the FAS.

6.4. Demographic and Other Baseline Characteristics

6.4.1. Demographic Characteristics

Demographic characteristics will be summarized for the FAS for Part A (overall) and Part B by treatment group and overall as described below. All missing data will be presented as part of a missing category. Standard descriptive statistics will be presented for the continuous variables of:

• Age (years)

Total counts and percentages of subjects will be presented for the categorical variables of:

• Age group (years):

o <65

- ∘ ≥65
- Sex
- Ethnicity
- Race

Demographic characteristics will be listed for the FAS for Part A (overall) and Part B by treatment group.

6.4.2. Baseline Characteristics

Baseline characteristics will be summarized for the FAS for Part A (overall) and Part B by treatment group and overall as described below. All missing data will be presented as part of a missing category.

Standard descriptive statistics will be presented for the continuous variables of:

- Disease duration (years)
- Number of previous systemic treatments
- Height (cm)
- Weight (kg)
- Body mass index (kg/m^2)
 - calculated as (body weight / height²) where weight is in kg and height is in m, and presented to one decimal precision
- Body Temperature (degrees Celsius)
- Respiration Rate (breaths per minute)
- Systolic Blood Pressure (SBP [mmHg])
- Diastolic Blood Pressure (DBP [mmHg])
- Heart Rate (beats per minute [bpm])
- Time Since Diagnosis with HS (calculated as year IC signed minus year of diagnosis, plus 1)
- AN Count Total Number of abscesses plus inflammatory nodules
- Number of Abscesses
- Number of Inflammatory Nodules
- Number of Draining Fistulae
- Number of Non-draining Fistulae
- Number of total Fistulae (Draining plus Non-draining)
- HADS total score
- HADS-Anxiety
- HADS-Depression
- HS-PGA
- Erythema Score
- DLQI total score
- IHS4
- EQ-5D-3L (Domain Scores, Index Score, and VAS Score)

• SF-12 (Physical Component Score and Mental Component Score) (see Appendix 2 for scoring method)

Total counts and percentages of subjects will be presented for the categorical variables of:

- Hurley Stage (II, III)
- Prior Biologic/Janus Kinase (JAK) Inhibitor Use for HS (yes/no)
- Alcohol (Never, Former, Current)
- Nicotine (Never, Former, Current)
- Presence of draining fistulae at baseline (yes/no)

The subject's Hurley Stage and erythema score (see Appendix 2 for scoring method) will be the worst reported for any anatomical region for that subject. Baseline characteristics will be listed for the FAS.

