4.1.6. Study Duration for Subjects

The maximum planned length of participation in the study for an individual subject is up to 49 weeks, which includes the following:

- Screening period of up to 28 days (4 weeks)
- 31-week treatment period
- Follow-up visit at Week 45

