5.1. Inclusion Criteria

Subjects are eligible to be included in the study only if all of the following criteria apply:

General

- 1. Subject has provided signed informed consent including consenting to comply with the requirements and restrictions listed in the informed consent form (ICF) and in this protocol.
- 2. Subject must be ≥ 18 (or the legal age of consent in the jurisdiction in which the study is taking place) and ≤ 75 years of age, at the time of signing the informed consent.

Type of Subject and Disease Characteristics

- 3. Diagnosis of HS for ≥ 1 year prior to first dose of study drug.
- 4. Hidradenitis suppurativa lesions present in ≥ 2 distinct anatomic areas (eg, left and right axilla; or left axilla and left inguino-crural fold), one of which is Hurley Stage II or Hurley Stage III at screening and Day 1 prior to enrollment/randomization.
- 5. A total AN count of \geq 5 at screening and Day 1 prior to enrollment/randomization.
- 6. Subject must have had an inadequate response to oral antibiotics (defined as ≥ 3-month treatment with an oral antibiotic for treatment of HS) OR exhibited recurrence after discontinuation to, OR demonstrated intolerance to, OR have a contraindication to oral antibiotics for treatment of their HS as assessed by the investigator through subject interview and review of medical history.
- 7. Must agree to use daily (throughout the duration of the study) one of the following over-the-counter topical antiseptics on their body areas affected with HS suppurativa lesions: chlorhexidine gluconate, triclosan, benzoyl peroxide, or diluted bleach in bathwater.
- 8. Subject must be willing to complete a daily skin pain diary 7 consecutive days prior to Day 1; if skin pain diaries are not completed for at least 3 of the 7 consecutive days prior to the Day 1 visit, the subject may not be enrolled/randomized.

Other Inclusions

- 9. No known history of active tuberculosis.
- 10. Subject has a negative tuberculosis test at screening, as defined by 1:
 - Negative QuantiFERON test OR
 - Negative purified protein derivative (PPD) test (< 5 mm of induration at 48 to 72 hours after test is placed).

- Subjects with a positive PPD test and a history of Bacillus Calmette-Guerin vaccination will be allowed with a negative OuantiFERON test.
- Subjects with a positive or indeterminate QuantiFERON test are allowed if all of the following is satisfied:
 - No symptoms of tuberculosis as determined by investigator.

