5.2. Exclusion Criteria

Subjects are excluded from the study if any of the following criteria apply:

Medical Conditions

- 1. Draining fistula count of > 20 at screening or Day 1 prior to enrollment/randomization.
- 2. Outpatient surgery ≤ 8 weeks prior or inpatient surgery ≤ 12 weeks prior to enrollment/randomization.
- 3. Other active skin disease or condition (eg, bacterial, fungal or viral infection) that could interfere with study assessments.
- 4. Active IBD within 3 years prior to enrollment.
- 5. Chronic pain not associated with HS (eg, fibromyalgia).
- 6. Uncontrolled, clinically significant system disease such as diabetes mellitus, cardiovascular disease including moderate to severe heart failure (New York Heart Association class III/IV), moderate to severe renal disease, moderate to severe liver disease or hypertension, as determined by investigator.
- 7. History of demyelinating disease (including myelitis) or neurological symptoms suggestive of demyelinating disease.
- 8. Malignancy within 5 years except treated and considered cured cutaneous squamous or basal cell carcinoma, in situ cervical cancer, or in situ breast ductal carcinoma.
- 9. The subject is at risk of self-harm or harm to others as evidenced by past suicidal behavior or endorsing items 4 or 5 on the Columbia-Suicide Severity Rating Scale (C-SSRS) assessed at screening. Subjects with major depressive disorder are permitted in the study if they are considered by the investigator to be stable and are taking no more than 1 medication. Subjects must have been on a stable dose within the 3 months prior to the first dose of study drug.
- 10. History or evidence of any clinically significant disorder (including psychiatric), condition, or disease that, in the opinion of the investigator, may pose a risk to subject safety or interfere with the study evaluation, procedures, or completion.

- 11. Exclusion criterion removed with Amendment 1 because it was a duplicate with Exclusion criterion 9.
- 12. Do not capture Exclusion 12, please select from 13, 14, or 15. Active infection or history of infection as follows:
- 13. Any active infection for which oral anti-infectives (antibiotics, antivirals, antifungals) were used ≤ 14 days prior to first dose of study drug (except for the use of a stable dose allowable antibiotics [doxycycline or minocycline only] for HS).

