 - Descriptive MMRM analyses will be performed by randomized treatment group, for change from baseline of IHS4 score and draining fistula count at Week 24 and Week 32. The change from baseline value will be used as the response variable, with baseline value, visit week, treatment, and treatment * visit week interaction included as predictors in the model. Estimated LSMean change from baseline, corresponding SE values, and 95% confidence intervals will be presented in the table summaries.

- The subgroup of subjects who were responders at Week 16 by AN count of 0, 1, or 2 (among those with Hurley stage II at baseline) will also be evaluated at Week 24 and Week 32 in the same manner as described for HiSCR75 responders.
- The subgroup of subjects who were non-responders at Week 16 by HiSCR75 will also be evaluated at Week 24 and Week 32 in the same manner as described for HiSCR75 responders.
- The subgroup of subjects who were non-responders at Week 16 by AN count of 0, 1, or 2 among those with Hurley stage II at baseline will also be evaluated at Week 24 and Week 32 in the same manner as described for the HiSCR75 responders.
- McNemar test will be used to evaluate the relationship between HiSCR75 response at Week 16 vs various response criteria at Week 32. P-values will be provided for descriptive purposes. The following response criteria at Week 32 will be used for this analysis:
 - o HiSCR75
 - o HiSCR90
 - HiSCR100
 - o HiSCR50
 - $\circ \quad \text{AN count of } 0, 1, \text{ or } 2$
- McNemar test will be used to evaluate the relationship between "AN count of 0, 1, or 2" response at Week 16 vs various response criteria at Week 32. P-values will be provided for descriptive purposes. The following response criteria at Week 32 will be used for this analysis:
 - o HiSCR75
 - HiSCR90
 - HiSCR100
 - HiSCR50
 - AN count of 0, 1, or 2

The following analyses will be done (by randomized treatment groups) for only the FAS subjects randomized to placebo who had least one dose of izokibep in Period 2 of the study AND who had a total AN count of \geq 5 at Week 16 and HS lesions present in at least 2 distinct anatomic areas (to correspond to the inclusion criteria), to address the question of how subjects respond to izokibep after 16 weeks of placebo, when they still meet original eligibility criteria:

- The baseline characteristics summary described in section 6.4.2 will be repeated for this analysis set at Week 16.

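### SAP 6.4.2 adds a year to time since HS diagnosis, so a descriptive baseline row runs too long; separately, the SAP 6.6.7 placebo-switcher set applies only part of the eligibility criteria it is said to represent

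*SAP*

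**What the plan says.** **Time since diagnosis.** SAP 6.4.2 gives the derivation as "Time Since Diagnosis with HS (calculated as year IC signed minus year of diagnosis, plus 1". The same list of continuous variables also contains "Disease duration (years", in years, with no formula. Protocol 5.1, inclusion criterion 3, requires "Diagnosis of HS for ≥ 1 year prior to first dose of study drug". Protocol 4.1.6 allows a "Screening period of up to 28 days (4 weeks", so consent can precede first dose by up to four weeks. Eligibility has its own summary in SAP 6.2: "Number and percentage of subjects who met/did not meet all eligibility criteria, together with the criteria not met".

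**Placebo switchers.** SAP 6.6.7 defines a Period 2 subset of placebo subjects who received izokibep, had an AN count of at least 5 at Week 16, and had "HS lesions present in at least 2 distinct anatomic areas (to correspond to the inclusion criteria". Its stated purpose is to show how subjects respond to izokibep after 16 weeks of placebo while they continue to satisfy the eligibility criteria they entered under. In the protocol, inclusion criterion 4 pairs the two-area requirement with a severity requirement, "one of which is Hurley Stage II or Hurley Stage III at screening and Day 1 prior to enrollment/randomization". Exclusion criterion 1 is "Draining fistula count of > 20 at screening or Day 1 prior to enrollment/randomization".

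**The concern.** Adding 1 is the right convention when days are counted inclusively, as the SAP does for relative day (5.1.1) and exposure duration (6.7.1). It has no such role in a difference of calendar years that is labelled as elapsed time and summarised as a continuous variable. Followed as written, the SAP would produce a disease-chronicity figure that is too long, in the population table of a study intended as one of two adequate and well-controlled trials.

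For the switcher subset, the stated question and the selection rule do not match. The rule stops halfway through inclusion criterion 4 and leaves out the fistula limit. A subject with no Stage II or III area at Week 16, or with a fistula count above the limit, would still be counted.

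**Working it through.** The plan gives a derivation and no numerical result, so there is no figure to reproduce.

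**Part 1: error of the formula.** Let consent fall at Y1 + u1 and diagnosis at Y0 + u0, where Y is the calendar year and u (0 ≤ u < 1) is the fraction of that year elapsed.

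- True elapsed time = (Y1 − Y0) + (u1 − u0)
- SAP value = (Y1 − Y0) + 1
- Error = 1 − u1 + u0, which is always above 0 and below 2
- Error without the added year = u0 − u1, which lies between −1 and +1

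The mean error is 1 − E[u1] + E[u0]. The documents give no dates, so a pattern must be assumed. Diagnosis dates are taken as spread over the year, so E[u0] is about 0.5.

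| Assumed consent dates | E[u1] | Mean error by formula | By simulation |
|---|---|---|---|
| Even over the year | 0.500 | 1 − 0.500 + 0.5 = 1.000 | 1.000 |
| All January to March | 0.125 | 1 − 0.125 + 0.5 = 1.375 | 1.378 |
| All October to December | 0.875 | 1 − 0.875 + 0.5 = 0.625 | 0.631 |

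The simulation used 2,000,000 draws restricted to subjects with at least 1 year to first dose. Durations were exponential: means of 3, 7 and 15 years all gave 1.000 under even spread, and the two clustered rows used a mean of 7. The value was too long in every draw. Without the added year, the mean error under even spread was 0.00.

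Worked cases:

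| Diagnosis | Consent | True years | SAP value | Without the added year |
|---|---|---|---|---|
| 30 Jun 2013 | 30 Jun 2023 | 10.00 | 11 | 10 |
| 15 Dec 2022 | 15 Jan 2023 | 0.08 | 2 | 1 |
| 15 Jan 2023 | 15 Mar 2023 | 0.16 | 1 | 0 |
| 1 Jan 2022 | 31 Dec 2022 | 1.00 | 1 | 0 |

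The smallest value the formula can return is 1, when both dates fall in the same calendar year.

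**Part 2: the switcher subset against the protocol.**

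| Protocol disease criterion | Applied at Week 16 in SAP 6.6.7? | Collected at Week 16 (protocol 1.3)? |
|---|---|---|
| AN count ≥ 5 (inclusion 5) | Yes | Yes, lesion count |
| Lesions in ≥ 2 areas (inclusion 4, first half) | Yes | Yes, lesion count |
| One area at Hurley Stage II or III (inclusion 4, second half) | No | Yes, Hurley staging |
| Draining fistula limit (exclusion 1) | No | Yes, lesion count |

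SAP 6.6.7 itself uses Week 16 Hurley stage and Week 16 fistula counts in the endpoints for this subset, so both inputs are treated as available. It also repeats the 6.4.2 baseline table at Week 16, and that table has Hurley categories II and III only. A subject below Stage II at Week 16 would have no category.

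The subset is drawn from Groups 1 and 2, planned at 28–29 each, so it has at most 56–58 subjects. The documents give no basis for counting how many would fail the two omitted criteria.

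**The case against.** **Limited consequence.** The formula is disclosed and identical in every arm. Time since diagnosis is not a stratification factor (SAP 3.1.5), an imputation predictor (6.6.2), a subgroup (6.6.6) or an input to any test. This stands: the effect is on the description of the population only.

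**Eligibility.** Because the minimum value is 1, a reader might infer that the formula lets every subject pass inclusion criterion 3, or hides ineligible subjects. The documents do not support that. Investigators assess eligibility, protocol section 5 bars waivers, SAP 6.2 reports and lists criteria not met, and SAP 6.3 covers deviations. The criterion also runs to first dose, while the formula runs to consent. For the same reason, a year difference of 0 should not be used as a deviation flag. Diagnosis on 5 Jan 2022, consent on 20 Dec 2022 and first dose on 10 Jan 2023 gives a difference of 0, yet 370 days have passed by first dose. In the other direction, about half of subjects with under 1 year of disease at consent would have a year difference of 1 and be missed (49.9% in a simulation with uniform dates).

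**Residual rounding.** Deleting the added year does not make single values exact. The SAP version is nearer the truth when u1 − u0 exceeds 0.5, which under independent uniform dates has probability 0.5 × 0.5² = 12.5%. This also stands; the deletion removes the systematic error, and only fuller dates remove the rounding.

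**Switcher subset.** The SAP states its two conditions openly, and its bracketed note mentions only inclusion criteria, whereas the fistula limit is an exclusion. The reference to the original criteria cannot be literal, since exclusion 33 bars anyone already randomized to this study. That supports relabelling as an adequate remedy. It does not explain the Hurley omission, because that requirement is part of an inclusion criterion. A reader might infer that the subset is materially contaminated; nothing in the documents shows this. Stages II and III are defined by tracts, with scarring in II (protocol 8.1.3), so loss of that status over 16 weeks on placebo is probably uncommon.

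**Conclusion.** The derivation in SAP 6.4.2 is wrong and overstates time since diagnosis for essentially every subject, by more than 0 and less than 2 years. A mean overstatement of 1 year rests on an assumed even spread of dates; about 0.6 to 1.4 years covers consents clustered at either end of the year. The consequence is one misstated descriptive row, similar across arms, with no effect on eligibility decisions or on any test. The separate entry for disease duration, without a formula, leaves it unclear whether a second measure exists.

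The SAP 6.6.7 point is minor. The subset does not match its description, but it is descriptive, has at most 56–58 members, and probably few of them would be affected.

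**What to change.** In SAP 6.4.2:

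- Delete the added year.
- Where full or month-level diagnosis dates are collected, derive elapsed time from them; otherwise use the plain difference of calendar years.
- State whether disease duration is the same quantity. If it is, keep one entry; if not, define it.

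In SAP 6.6.7, do one of the following:

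- Also require at Week 16 at least one area at Hurley Stage II or III and a draining fistula count within the protocol's limit. The protocol states that limit in two ways: the synopsis (1.1) excludes counts of ≥ 20, while exclusion criterion 1 excludes counts of > 20. These passages must be reconciled before the rule is programmed.
- Or keep the rule and describe the set as subjects meeting the AN-count and two-area criteria at Week 16, without claiming that they meet the original eligibility criteria.

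The cost is a few lines of SAP text and programming. No new data are needed. Under the first 6.6.7 option the subset may become slightly smaller.
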